After the participants in the CommitFit and CommitFit\$ groups download the app, they will be shown how to pick a health behavior (fruits/vegetables, water, decreased sugary beverages, physical activity, sleep) and then set a goal and a time period to work on their goal. They will receive a daily reminder to log their health behaviors. At the end of their goal period, they will be rewarded with points for logging behaviors and successfully achieving their goals. Points will be used to rank the participant on the leaderboard using the username that they registered with. Users will be encouraged not to use or share their real names or any identifying personal information. Users can also use points to unlock gear for their avatar in the gear store. It will take less than 15 minutes to download and learn CommitFit and less than 1 minute each day to log their behavior. Control group participants will receive email handouts with healthy lifestyle tips which they could use if they choose to. They will not use the CommitFit app. All participants will be compensated through eGift cards.

Software analytics will be utilized to evaluate how the app was used (frequency of goals set and behaviors logged), duration of use, etc., to evaluate app features and gamification techniques. We will evaluate changes in health behaviors using online surveys, and measure health metrics (height and weight which will be used to calculate Body Mass Index (BMI), and blood pressure) in the clinic.

In the CommitFit and CommitFit\$ groups, we will have the adolescents take 7 surveys-GAD7, PedQL, Reasons why I think about being healthy, Behavior economics survey, Gamification Survey, CommitFit App Survey, and Commercialization Survey for adolescent subject. Each clinic visit will last from 30 to 60 minutes. Similarly, we will have the caregivers take 4 surveys Gamification Survey, CommitFit App Survey, Behavior economics survey, and Commercialization Survey for caregiver subject. In the control group, adolescents will only take 4 surveys- GAD7, PedQL, Reasons why I think about being healthy, and Behavior economics survey. Caregivers in the control group will take only the Behavioral Economic survey. All participants will take the surveys at the beginning of the study, after end of 3rd month, and at the

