end of the 4th month (follow-up visit). All surveys will be available in online and paper format and will take 15 to 30 minutes to complete per participant. Weight, height and blood pressure from all adolescents and their caregivers will also be collected at the clinical site. If your adolescent chooses to stop participating in the study before its completion, you can still remain enrolled in the study, and you will take surveys and clinic visits at the end of 3rd and 4th months. All participants will complete the 5-10 minute paper exit survey at their final 4-month clinic visit.

We will use logic and branching reasoning in Redcap that would allow participants to skip questions. Participants can skip questions that they do not want to answer and can submit without getting an error message if a question is left blank. Questions will include demographics, environmental factors that could influence health behaviors, and technology and mHealth app use. We will be measuring changes in health behaviors (physical activity, water, sugary beverages, fruits/vegetables, and sleep) by analyzing data logged into the app.

There will be three groups (1) Control (2) CommitFit group using the app where the intervention will not include extra monetary incentives and (3) CommitFit\$ group using the app which will be pushed with extra monetary incentives. 30 adolescents will be randomly assigned to three groups with each group having 10 adolescents. Their respective caregivers will also join the same groups as their adolescents. Participants will download the app on their iPhone or iPad and if the participant doesn't have either of them, an iPad will be temporarily provided for the time participants are in the study which will be returned to the researchers after the study, we will use a spreadsheet to capture all the information in one place for each participant.

The purpose of this study is to evaluate “CommitFit” a smart phone app to help teens develop and maintain positive health behaviors. We will be measuring changes in health behaviors (physical activity, water, sugary beverages, fruits/vegetables, and sleep) in CommitFit and CommitFit\$ groups. The app will only be tracking goal progress and nothing else.

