- In the control group (10 adolescents, randomly chosen and their caregivers), we will email handouts with healthy lifestyle tips which participants could use if they choose to. During this time there will be no CommitFit app use by participants. They will also not receive any extra monetary incentives.
- In the CommitFit group, participants (10 adolescents, randomly chosen, and their caregivers) will use regular CommitFit app without extra monetary incentives.

Researchers will assist participants to download the CommitFit app. Participants will be asked to use the app for *3 months*, there will be no penalties if they don't use the app for the entire duration or only use it frequently. The adolescents and their caregivers will get an app reminder each day to update their health behavior goals once in morning (8 am) and once in the evening (5pm) on which the participant will spend approximately 1 min in a day.

- In CommitFit\$ group, participants (10 adolescents, randomly chosen and their caregivers) will use the CommitFit app just as the CommitFit group for 3 months. In addition to the eGift cards, adolescents will receive 5 cents for every point they earn during the study. There are a maximum of 1050 possible points that can be earned, so the most they can receive is \$52.50 in cash at the end of 3rd month of their participation in this CommitFit\$ group. This will be calculated by tracking the points at the beginning and end of each month for the CommitFit\$ group. Only adolescents will receive these extra monetary incentives as this group is set up to simulate adolescent app users receiving incentives from their caregivers for adopting healthy lifestyle behaviors in the real world. For all three groups (Control, CommitFit and CommitFit\$) – participants – adolescents and their caregivers will come to the clinic and have their height, weight, and blood pressure measured at the beginning of the study, after the third month, and after the fourth month (follow-up visit). These will be conducted in a private exam or conference room by research staff, and for adolescents their caregivers will also be present.

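### Cash per point in CommitFit$ rewards the same self-entered log that is a stated measure of behaviour change, so a CommitFit$ versus CommitFit difference in logged behaviour can come from reporting alone

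*Combined protocol and SAP*

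**What the plan says.** All of the following is in Section VII (Study Procedures/Study Design) unless noted.

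- **Behaviour measure.** "We will be measuring changes in health behaviors (physical activity, water, sugary beverages, fruits/vegetables, and sleep) by analyzing data logged into the app". A later paragraph says these changes are measured in the CommitFit and CommitFit$ groups.
- **How the log is filled.** Participants enter it themselves after a reminder. The stated burden is "less than 1 minute each day to log their behavior". On scope: "The app will only be tracking goal progress and nothing else". No sensor, caregiver confirmation or audit of entries is described.
- **What earns points.** At the end of a goal period, "they will be rewarded with points for logging behaviors and successfully achieving their goals". This applies to both app arms, which also share the leaderboard and the avatar gear.
- **What differs between the app arms.** In CommitFit$, "adolescents will receive 5 cents for every point they earn during the study". The ceiling is stated: "There are a maximum of 1050 possible points that can be earned". For the other app arm: "In the CommitFit group, participants (10 adolescents, randomly chosen, and their caregivers) will use regular CommitFit app without extra monetary incentives". Section X (Compensation) repeats the $52.50 maximum.
- **Second source for behaviour.** "We will evaluate changes in health behaviors using online surveys". Section I says the same about surveys.
- **Analysis.** Section XV (Statistical Analysis Plan) applies chi-square tests and t-tests at p<0.05 to study outcomes. It does not mention unlogged days, differential reporting, or which behaviour source takes precedence.

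**The concern.** CommitFit$ versus CommitFit is the comparison that isolates the cash. In that comparison one randomised arm is paid for producing its own outcome data and the other is not. Randomisation does not protect against this, because the payment acts on measurement after assignment.

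There are two routes. Payment can raise the number of days logged, and it can raise the number of goals logged as met when they were not. Either can move a log-based behaviour summary while behaviour stays the same. A statement that cash incentives improve health behaviours would then not follow from the log data.

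This problem is separate from Control having no log. It would remain if the trial had only the two app arms.

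**Working it through.** **1. The plan's own figure.** 1050 points × $0.05 = $52.50, as stated. Gift cards total 3 × $50 = $150 per participant, so the extra cash is 52.50 / 150 = 35% on top. Over an assumed 90 days of app use it is 52.50 / 90 = $0.58 a day at most.

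**2. False success entries.** The documents give no misreporting rate, goal-met rate or SD, so these are assumptions: 10 adolescents per arm (Section VII), 90 days, 50% of days truly on goal in both arms, between-person SD of 20 percentage points, two-sided two-sample t-test at 0.05, and no true effect. If f$ and f0 are the shares of missed days falsely logged as met in CommitFit$ and CommitFit, then

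spurious difference = 0.50 × (f$ − f0).

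| f$ | f0 = 0: difference | p<0.05 | f0 = f$/2: difference | p<0.05 |
|---|---|---|---|---|
| 0% | 0 points | about 5% | 0 points | about 5% |
| 10% | 0.50 × 0.10 = 5 points | about 8% | 0.50 × 0.05 = 2.5 points | about 6% |
| 20% | 0.50 × 0.20 = 10 points | about 21% | 0.50 × 0.10 = 5 points | about 9% |
| 30% | 0.50 × 0.30 = 15 points | about 43% | 0.50 × 0.15 = 7.5 points | about 17% |

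The rejection rates are simulated. The right-hand columns matter because CommitFit adolescents also have non-cash reasons to log success, namely points, rank and gear.

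**3. Completeness alone, with no false entries.** Assume the same 50% true goal-met rate in both arms (varying between persons), 90 days, and unlogged days counted as not met. The expected difference is 0.50 × (difference in mean completeness). Logging varies widely between persons in this simulation.

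- 50% v 50% of days logged: 0 points, p<0.05 about 5% of the time.
- 50% v 65%: 0.50 × 0.15 = 7.5 points, about 17%.
- 50% v 80%: 0.50 × 0.30 = 15 points, about 50%.

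**4. Direction.** Points are also earned simply for logging, so cash may bring in bad days that an unpaid adolescent leaves blank. Assume 50% of days are truly on goal, the unpaid arm logs 80% of good and 40% of bad days, and the paid arm logs 90% of both.

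- Success per logged day, unpaid: (0.50 × 0.80) / (0.50 × 0.80 + 0.50 × 0.40) = 0.40 / 0.60 = 67%.
- Success per logged day, paid: 0.45 / 0.90 = 50%. This is a bias against the incentive.
- Blank days counted as not met: 0.50 × 0.80 = 40% unpaid v 0.50 × 0.90 = 45% paid. This is a bias in its favour.

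The same logging behaviour gives opposite signs, depending on a metric and a blank-day rule that the documents do not define.

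**5. Whether the surveys fill the gap.** Section VII names seven adolescent surveys for the app arms: GAD7, PedQL, reasons for thinking about being healthy, behaviour economics, gamification, the app survey and commercialization. None is described as measuring physical activity, water, sugary beverages, fruits and vegetables, or sleep. The stated question content covers demographics, environmental factors, and technology and app use. The only sentence that lists the five behaviours together with a data source names the app log.

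**The case against.** **The log is not the only behaviour source.** This stands. A reader might infer that the log is the sole behaviour outcome, but Sections I and VII both name surveys. Section VII also assigns the frequency of goals set and behaviours logged to evaluating app features. Part of the separation proposed below is therefore already in the text, and the sentence on logged data cuts across it. What does not follow is that the surveys resolve the problem, since none is shown to cover the five behaviours.

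**The bias need not favour the incentive.** This also stands. A reader might infer that paid logging must flatter CommitFit$. It does so if false success is logged or blank days count as not met, which is the more likely pattern, but step 4 shows that it can reverse. The split of points between logging and achieving goals is not stated either, so the reward for a false success cannot be worked out.

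**Incentives are the intervention, and this is a pilot.** Cash per point is deliberate: it is meant to simulate incentives from caregivers. More logging is a legitimate engagement effect of it. Section I frames the work as a feasibility and pilot study, and Section XV names neither a primary outcome nor this contrast. Against that, Section VII states a purpose of measuring behaviour change in the two app groups, and Section XV tests study outcomes at p<0.05. The objection limits the harm to reading the log as behaviour; it does not remove it.

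**Clinic measures are unaffected.** True of BMI and blood pressure, which research staff measure in all arms. They are health metrics, not measures of the five behaviours.

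**Conclusion.** The point holds as a structural one. With points tied to logging and goal attainment, cash tied to points in one arm only, no described check of entries, and the same log named as a behaviour measure, a CommitFit$ versus CommitFit difference in logged behaviour cannot be separated from paid differences in reporting.

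Its size and direction are not established by the documents. The rejection rates of about 8%, 21% and 43% assume that CommitFit misreports nothing. At half the CommitFit$ rate they fall to about 6%, 9% and 17%. All rest on the assumed goal-met rate, SD and misreporting rates. A reader might take the 43% as an expected false-positive rate; it is only the top of an illustrated range. The problem concerns the reading of the logs as behaviour. It does not affect their use as engagement data, or BMI and blood pressure.

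**What to change.** In Section VII and the SAP:

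1. State that for CommitFit$ versus CommitFit the app logs (days logged, goals set, goals logged as met, points) are engagement outcomes only and will not be reported as change in health behaviour.
2. Base any behaviour conclusion for this contrast on survey items that earn no points and are taken identically in both app arms at baseline, month 3 and month 4. Name the existing items that cover the five behaviours.
3. If no existing items cover them, make no behaviour claim for this contrast, and report BMI and blood pressure as health metrics only.
4. Tell CommitFit$ families that survey answers do not affect payment.

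The change is one of wording plus a short statement to families. It needs no further participants or visits, and the incentive itself is untouched. The cost is in what can be claimed: the incentive contrast loses its log-based behaviour result, and loses any behaviour result if the existing surveys do not cover the five behaviours.

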B. Control of access to scientific data: All data will be shared within IRB and HIPAA-approved parameters. The PI will monitor and restrict access of identified data to IRB-approved staff. All significant contributors to the data will be credited. Deidentified data submitted to MOspace and upon request, will be publicly accessible.

Data that are unable to be sufficiently deidentified will not be made available for sharing, to protect the identity of the participant. Although the final dataset will have identifiers removed prior to release for sharing, because of the small sample size, we believe that there remains the possibility of deductive disclosure of subjects with unusual characteristics. Data that cannot be sufficiently deidentified will not be shared.

Element 5: Oversight of Data Management and Sharing: Study Principal Investigator, [name], will be responsible, before, during, and after the study, for data collection, management, storage, and sharing. She will maintain the Data Management and Sharing Plan with updates when necessary. At the conclusion of the study, [name] will deposit all deidentified data and corresponding documentation into MOspace and destroy any identified data not required for additional analysis or publications and in compliance with IRB protocols

XV. Statistical Analysis Plan

Descriptive statistics were used to examine baseline demographics and to examine study outcomes over time between study arms. Chi-square analysis was used to compare group differences for categorical outcomes and t-test for continuous outcomes for baseline demographics and BMI, as well as study outcomes. An a priori value of $p < 0.05$ was set for statistical significance.

XVI. References

1. Maternal and Child Health Bureau. Child Health USA 2014: Adolescent overweight and obesity. U. S. Department of Health and Human Services and Health Resources and Services Administration. <https://mchb.hrsa.gov/chusa14/health-status-behaviors/adolescents/adolescent-overweight-obesity.html>. Published 2014. Accessed2020.
2. An R. Projecting the impact of the coronavirus disease-2019 pandemic on childhood obesity in the United States: A microsimulation model. *J Sport Health Sci.* 2020;9(4):302-312. DOI:10.1016/j.jshs.2020.05.006.

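### Section XV tests continuous outcomes with an unadjusted t-test and does not say whether follow-up or change is compared; a three-arm ANCOVA on baseline would settle the choice and usually narrow the intervals.

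*Combined protocol and SAP*

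**What the plan says.** Section XV (Statistical Analysis Plan) is three sentences long. For continuous data it gives a "t-test for continuous outcomes for baseline demographics and BMI, as well as study outcomes", with significance at p < 0.05. The same section uses descriptive statistics "to examine study outcomes over time between study arms", so the time dimension is attached to description and not to a test.

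Section VII (Study Procedures/Study Design) sets out the data:

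- **Arms.** "30 adolescents will be randomly assigned to three groups with each group having 10 adolescents"; each adolescent's caregiver joins the same arm.
- **Clinic measures.** Height, weight and blood pressure are taken in adolescents and caregivers of all three arms at the start, after month 3 and after month 4.
- **Survey timing.** "All participants will take the surveys at the beginning of the study, after end of 3rd month", and again at month 4.
- **Surveys given to every arm.** For adolescents: "In the control group, adolescents will only take 4 surveys- GAD7, PedQL, Reasons why I think about being healthy, and Behavior economics survey". For caregivers: "Caregivers in the control group will take only the Behavioral Economic survey".
- **Aim.** "We will evaluate changes in health behaviors using online surveys, and measure health metrics". This suggests change scores, but no section ties a change score to a test of BMI, blood pressure or a survey.
- **Blanks.** "Participants can skip questions that they do not want to answer and can submit without getting an error message" when a question is left empty.

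**The concern.** Two things are at stake.

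**The tested quantity is open.** A t-test on the month-3 value, on the month-4 value, or on the change to either visit would each comply with Section XV. Two analysts following the text faithfully could reach different verdicts on the same data. If the quantity is settled once results are visible, the nominal 5% no longer holds.

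**Precision is left unused.** With 10 per arm there is little to spare. Which t-test is the more precise depends on the correlation r between baseline and follow-up. The documents do not give r, and it may differ by outcome. A follow-up test ignores the baseline altogether. A change score subtracts all of it, which adds noise when r is low. ANCOVA estimates how much of the baseline to remove, so r need not be known beforehand. In a pilot the benefit shows mainly as narrower confidence intervals.

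The point covers outcomes with a baseline in every arm: BMI, blood pressure, and the surveys that controls also complete. App-logged behaviors and app-only surveys have no control values and lie outside it.

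**Working it through.** The plan contains no power or precision figure to reproduce.

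**Inputs.** From the documents: three arms, n = 10 per arm, p < 0.05. Assumed: a two-sided test, complete data, equal SDs at baseline and follow-up, and r from 0 to 0.95. All differences are in units of the follow-up SD. Variance is pooled over three arms for every method, so the comparison is like for like.

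**Standard error of a difference between two arms**

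- Follow-up: √(2/10) = 0.447; 30 − 3 = 27 df.
- Change: 0.447 × √(2(1 − r)); 27 df.
- ANCOVA: 0.447 × √(1 − r²) × √(1 + 1/25); 30 − 4 = 26 df. The last factor allows for chance baseline imbalance and equals 1.02, the 2% cost at r = 0.

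**95% CI half-width** = t × SE, with t = 2.052 on 27 df and 2.056 on 26 df. Follow-up: 2.052 × 0.447 = 0.92. At r = 0.7, change: 0.918 × √0.6 = 0.71; ANCOVA: 2.056 × 0.447 × 1.020 × √0.51 = 0.67.

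**Detectable difference at 80% power**, from the noncentral t: 1.30 for follow-up, 1.30 × √(2(1 − r)) for change, and 1.33 × √(1 − r²) for ANCOVA.

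| r (assumed) | Half-width: follow-up | change | ANCOVA | Detectable: follow-up | change | ANCOVA |
|---|---|---|---|---|---|---|
| 0 | 0.92 | 1.30 | 0.94 | 1.30 | 1.84 | 1.33 |
| 0.3 | 0.92 | 1.09 | 0.89 | 1.30 | 1.54 | 1.27 |
| 0.5 | 0.92 | 0.92 | 0.81 | 1.30 | 1.30 | 1.15 |
| 0.7 | 0.92 | 0.71 | 0.67 | 1.30 | 1.01 | 0.95 |
| 0.8 | 0.92 | 0.58 | 0.56 | 1.30 | 0.82 | 0.80 |
| 0.9 | 0.92 | 0.41 | 0.41 | 1.30 | 0.58 | 0.58 |
| 0.95 | 0.92 | 0.29 | 0.29 | 1.30 | 0.411 | 0.414 |

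Equal detectable differences occur at r = 0.20 (ANCOVA and follow-up) and r = 0.92 (ANCOVA and change). Between those values ANCOVA is the most precise of the three. Outside them its loss is at most 0.03 SD over the range shown.

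**Cost of the open choice.** Both t-tests were simulated on the same data, in two-arm trials with 10 per arm and 100,000 trials per setting. Each alone rejects 4.9–5.1% under the null.

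| r (assumed) | 0 | 0.5 | 0.7 | 0.9 | 0.95 |
|---|---|---|---|---|---|
| At least one rejects, no true effect | 8.4% | 9.2% | 9.5% | 9.7% | 9.8% |
| Verdicts differ, assumed true effect 0.8 SD | 27% | 33% | 41% | 59% | 60% |

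**Validity of ANCOVA.** In three-arm simulations all three methods reject 4.7–5.2% under the null.

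**Missing baseline scores.** If participants without a baseline are dropped, ANCOVA on 9 or 8 per arm beats a follow-up test on all 10 only for r above 0.39 or 0.51. A change score loses the same participants. Alternatively, the overall baseline mean can be filled in. With 2 of 10 per arm filled in (assumed, missing at random), the ANCOVA SE is 0.456, 0.410, 0.355 and 0.275 at r = 0, 0.5, 0.7 and 0.9, against 0.447 for follow-up, and null rejection is 4.7–5.0%.

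**The case against.** The strongest reply is that nothing here is an error. A single prespecified t-test of either kind is valid, and one added line naming the quantity and visit would close the open choice without ANCOVA. The study is a feasibility pilot with no stated power target for lost precision to defeat. If the protocol's references to change are read as change scores, the detectable difference improves by 0.15 SD at r = 0.5, 0.06 at 0.7 and almost nothing at 0.9. BMI over three to four months may well lie near that upper end (an assumption). With only two arms in each analysis, ANCOVA is marginally behind a change score at r = 0.9 (0.597 against 0.593 SD). The inflated false-positive rate arises only if both tests are run and the significant one is reported, which no section plans.

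Most of this is correct and limits the weight of the point. It does not remove it. Naming one t-test still requires a guess at r for each outcome, and a wrong guess is costly: 1.30 against 0.58 SD for a follow-up test at r = 0.9, or 1.54 against 1.27 SD for a change score at r = 0.3. ANCOVA avoids the guess for one degree of freedom. The plan also sets a significance threshold, pilot or not, so the tested quantity should be fixed.

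Two further remarks stand. ANCOVA does not settle multiplicity: three unadjusted pairwise contrasts on one outcome still give at least one false positive in about 12% of null trials. And the documents do not say that every common survey yields a continuous score.

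**Conclusion.** The concern holds as an inexpensive improvement to a valid but under-specified analysis. Section XV fixes neither the tested quantity nor the visit and uses no baseline, although baselines are collected in every arm for the outcomes named. Choosing between follow-up and change after seeing the data would raise the per-comparison false-positive rate to 8.4–9.8%. Relative to a follow-up test, ANCOVA lowers the detectable difference by 0.15 SD at r = 0.5 and 0.35 SD at r = 0.7, and raises it by 0.03 SD at r = 0. Relative to a change score it lowers it by 0.15 and 0.06 SD at r = 0.5 and 0.7, and the two are practically equal from about r = 0.9. These figures rest on 10 per arm, complete data, a two-sided 5% level and assumed values of r. No bias is claimed.

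**What to change.** In Section XV, for BMI, systolic and diastolic blood pressure, and each survey given to all arms that yields a continuous score, replace the t-test with one three-arm ANCOVA:

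- **Outcome:** the month-3 value, which closes the app period. Analyze month 4 the same way and label it secondary. The documents rank neither visit, so the investigators should confirm this order.
- **Terms:** arm and the participant's own baseline value.
- **Populations:** adolescents and caregivers in separate models.
- **Reporting:** adjusted mean differences between arms with 95% confidence intervals. State which contrasts are of interest; their multiplicity is a separate matter.
- **Missing baseline:** fill in the mean of the observed baseline values over all arms combined, separately for adolescents and caregivers, so that the participant stays in the model. This rule does not cover missing month-3 values, which need their own statement.

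The cost is SAP wording and standard software, with no added participants or visits. One degree of freedom is spent, and the SE is about 2% larger than for the follow-up test if r = 0. Section XV is written in the past tense. That alone does not show the analysis has been done, but the change should be dated before outcome data are examined, or else labelled post hoc.
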